6.4.4. Study Flow Chart

The schedule of visits is presented in [Table 6-1](#). After screening a minimum of eight and maximum 14 weeks between initiation of TG02-treatment and resection surgery is anticipated with a follow up period of 4 weeks after surgery.

Table 6-1: Schedule of visits

Week	Screening within 2 weeks	Treatment period (Pre-surgery) (weeks 1-6)					Wk 8±4 days Surgery	If Surgery Wk 8-10	If surgery is Wk 10	If Surgery Wk 10-14	End of study visit ^o Up to 6 wk after surgery
		1	2	3	4	6					
Day		1	8	15	22	36	50	51-63	64	65-92	See footnote ^o
Informed Consent	X										
Patient eligibility	X										
Pregnancy Test	X										
Medical History	X										
Physical Examination ^h	X	X		X		X	X		X		X
Vital Signs ^h	X	X	X	X	X	X	X		X		X
12-lead ECG	X										
ECOG ^h	X	X	X	X	X	X	X		X		X
DTH (TG02) test ^{j,q}		X			X	X	X ^b		(X ⁱ)		
Immunology Sample ^h (PBMC)		X					X ^e			X ^g	
TG02-treatment ^p (TG02/GM-CSF)		X	X	X	X	X			(X ^f)		
Pembrolizumab ^k					X	X	X ^s		X ^t		
Haematology ^h	X	X		X		X	X		X		X ⁿ
Biochemistry ^h	X	X		X		X	X		X		X ⁿ
CEA (biomarker)	X						X ^l		X ^g	X ^g	
CTC (Circulating Tumour Cells)		X					X ^l			X ^g	
CT chest/abdomen/ Pelvic	X										
MRI (if standard Hospital procedure (re-staging))	X	As indicated									
FDG PET/CT	X ^r						X ^g	X ^g	X ^g	X ^g	
Tumour Biopsy	X ^c										
Surgery and resection of tumour tissue ^m							X ^d	X ^d	X ^d	X ^d	
Adverse Events		Continuously									X ^a
Concomitant medications	X	Continuously									X ^a

- a: Deemed to be related to TG02-treatment
- b: If surgery is scheduled to be done in week 8, DTH (TG02) injection to be done approximately 48 hours prior to surgery.
- c: For patients receiving chemo-radiation before enrolment into study, core biopsy of target colorectal tumour should be taken after chemo-radiation and during the screening window (2 week) and as close as possible to the first TG02-treatment (day 1, week 1). For patients not having chemo-radiation before enrolment into the study, a core biopsy of target colorectal tumour can be taken within the last 4 weeks but as close as possible to the first TG02-treatment (day 1, week 1). If a pre TG02-treatment biopsy has been taken for diagnostic workup as hospital procedure, this biopsy, if adequate for the study specific immune analysis and no intervening treatment has been given, can also be used.
- d: Tumour tissue taken during resection. If for any reason, the patient will not have surgery a biopsy will be obtained if possible.
- e: To be done 2-0 days before surgery
- f: If surgery is scheduled for week 10, there will be no TG02-treatment given at week 10. If no surgery at week 10, the last TG02-treatment to be given at week 10.
- g: As close as possible up to the date of surgery.
- h: At the visits when TG02 and/or TG02-treatment (and pembrolizumab in Part II) is scheduled, the assessments should be performed prior to the treatments.
- i: Only to be taken for patients who have surgery after week 10 and had a negative DTH outcome at week 8. DTH (TG02) injection to be done 48 hours prior to surgery.
- j: Assessment of DTH (TG02) injection site to be done 48 hours (+/- 4 hours) after each DTH (TG02) injections by the patient in a study specific diary.
- k: Only applicable in Part II of the protocol
- l: To be done prior to surgery
- m: Allowed time for surgery (resection specimen) scheduled for week 8 is + 2 week and allowed time for surgery (resection specimen) scheduled for week 10 is + 4 week
- n: Blood samples for routine haematology and serum biochemistry to be recorded if already available in the patient medical record (standard of care)
- o: End of study visits to be scheduled during the hospitalized post-operative recovering period, up to 6 weeks after surgery.
- p: TG02-treatment is a combination of the two IMPs: GM-CSF and TG02. When TG02-treatment is administered, GM-CSF is to be given as an intradermal injection 15-30 minutes before the TG02 intradermal injection. GM-CSF and TG02 are administered as 2 separate intradermal injections, 15 to 30 minutes apart, at the same site in the upper arm. After any TG02-treatment the patients will be monitored for heart rate and blood pressure at 5, 10 and 30 minutes and then every 30 minutes thereafter for up to 2 hours post administration
- q: In addition, TG02 will, at certain time points, be administered intradermally (without prior administration of GM-CSF) in the lower area of the contra lateral arm as DTH test. The administration of GM-CSF (0.10 mL reconstituted GM-CSF) and TG02 (0.10 mL reconstituted TG02) has to be strictly intradermal.
- r: Should be within the last 4 weeks prior to first TG02-treatment.
- s: If surgery is scheduled after Day 50/Week 8, pembrolizumab will be given at Day 50/Week 8.
- t: If surgery is scheduled after Day 64/Week 10, a further pembrolizumab infusion will be given at Day 64/Week 10.

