Patients will be evaluated for safety at scheduled visits until surgery and at the end of study visit approximately 4 weeks after surgery. In addition, after any TG02-treatment the patients will be monitored for heart rate and blood pressure at 5, 10 and 30 minutes and then every 30 minutes thereafter for up to 2 hours post administration.

A FDG PET-CT will be performed before TG02-treatment is initiated (baseline scan should be within the last 4 weeks prior to first TG02-treatment) and a second scan as close as possible before surgery.

Tumour samples for assessment of immune response will be taken pre TG02-treatment in the form of a study specific biopsy and at time of surgery by analysis of the resected tumour tissue. If a pre TG02-treatment biopsy has been taken for diagnostic workup at the hospital, this biopsy, if adequate for the study specific immune analysis and no intervening treatment has been given, can be used as the study specific biopsy if taken within the last 4 week prior to first TG02-treatment. If for any reason the patient does not proceed to surgery, a biopsy will be obtained at the time of planned surgery if possible. In addition, archival biopsy samples from both initial staging (primary diagnosis) and re staging will be utilised, as needed. In the patient information sheet and informed consent form (PIS/ICF), patients will be asked to give consent to the use of archived biopsy material. These archival samples will be used to assess RAS-mutation status and other baseline immune assessments.

Delayed-Type Hypersensitivity (DTH) tests will be performed at week 1, week 4, week 6 and week 8 (if surgery is scheduled for week 8, the DTH test should be performed two days before surgery). If surgery is scheduled for after week 10, and the patient has had only negative DTH tests up to and including week 8, an additional DTH test should be performed at week 10.

Blood samples will be collected for in vitro assessment of TG02-specific immune responses (Immunology sample, PBMC) will be collected at baseline (Day 1, Week 1) and week 8 (Day 64). If surgery is scheduled to occur after week 10, a third sample will be taken as close as possible to the date of surgery.

In total, the study will enrol up to 16 patients for Part I and II.

Subject population: The target population is patients with locally advanced primary and recurrent oncogenic KRAS exon 2 mutant colorectal cancer eligible for radical pelvic surgery at time of enrolment.

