The treatment period will be from Day 1 (Week 1) and up to surgery, which is planned for week 8 but can occur in a window up to week 14. The following assessments will be performed on Day 1, Day 8, Day 15, Day 22, Day 36, Day 50 and if surgery is after week 10 (Day 64):

- Vital signs (heart rate, blood pressure and tympanic body temperature) and ECOG performance status
- Concomitant medications and adverse events will be monitored continuously
- Physical examination, haematology and serum biochemistry (Table 9-1) before treatment (Day 1) and during treatment on Day 15, Day 36, Day 50 and if surgery after week 10 (Day 64).
- TG02 treatment will be administered on Days 1, 8, 15, 22 and 36. If surgery after week 10 TG02 treatment will also be given at week 10 (Day 64).
- Pembrolizumab will be given on Days 22 and 36. If surgery is scheduled after Day 50/Week 8, pembrolizumab will be given at Day 50/Week 8. If surgery scheduled after Day 64/Week 10, a further pembrolizumab infusion will be given at Day 64/Week 10.
- DTH tests will be performed at baseline (Day 1), week 4 (Day 22), week 6 (Day 36) and week 8 (Day 50) (if surgery is scheduled for week 8 the DTH test should be performed two days before surgery). If surgery is after week 10, and the patient has had negative DTH tests up to and including week 8, an additional DTH test should be performed at week 10 (Day 64).

- Blood samples for in vitro assessment of TG02-specific immune responses (Immunology sample, PBMC) will be taken at baseline (Day 1) and Day 50. If surgery is after week 10, an additional sample should be taken as close as possible up to the date of surgery (see separate Immune monitoring plan).
- The CEA biomarker will be evaluated at Day 50. If surgery is after week 10 a third sample will be taken at Day 64 or just prior to surgery, whichever is the more appropriate.
- Tumour samples for assessment of immune response will be taken at time of surgery. If for any reason the patient will not have surgery a biopsy will be obtained if possible at the latest by week 14 (see separate Immune monitoring plan).
- FDG PET-CT scan for tumour assessment of standard uptake value (SUV-max) as close as possible up to date of surgery.
- Circulating Tumour Cells (CTC) will be evaluated at Day 1 and Day 50. If surgery is after week 10, an additional sample can be taken as close as possible up to the date of surgery.

Additional monitoring during the first 2 hours after any TG02-treatment:

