8.2. Dosing, Mode of Administration, Duration of Treatment

TG02 and GM-CSF will be given as intradermal injections by trained study staff authorized to do such procedures. Training of study staff will be performed by Sponsor before any patients are treated. In addition, the administration of TG02 and GM-CSF is described in the Study Drug Handling Plan (SDHP).

GM-CSF and TG02 are administered as 2 separate intradermal injections, 15 to 30 minutes apart, at the same site in the upper arm. In addition, TG02 will at certain time points be administered intradermally (without prior administration of GM-CSF) in the lower area of the contra lateral arm as DTH test.

The administration of GM-CSF (0.10 mL reconstituted GM-CSF) and TG02 (0.10 mL reconstituted TG02) has to be strictly intradermal. Utmost care has to be taken that no material is administered subcutaneously. When done correctly, a small bleb should appear following the injection. An injection that is too superficial will result in loss of volume from the injection site during injection or after withdrawal of the needle. The administration should be performed at the same site every time, if possible.

TG02: provided as a lyophilised solid powder for reconstitution in sterile water for injection to be given via intradermal injection.

TG02 given in the TG02-treatment will be administered in the upper arm at weeks 1, 2, 3, 4, and 6. If surgery is scheduled after week 10 one more TG02-treatment will be given in week 10. **TG02 is to be given 15-30 minutes after GM-CSF.**

TG02 will at certain time points (week 1, week 4, week 6, week 8 and possible week 10), be administered intradermally (without prior administration of GM-CSF) in the lower area of the contra lateral arm as a DTH test to evaluate the immunological response (see [Table 6-1](#)).

Where a DTH (TG02) injection is being performed the TG02 DTH dose should be administered **30 minutes** before the TG02-treatment and patients should be observed for at least 30 minutes after ALL TG02 treatments.

GM-CSF: provided as a lyophilised solid powder for reconstitution in sterile water for injection to be given via intradermal injection.

GM-CSF given in the TG02-treatment will be administered in the upper arm at weeks 1, 2, 3, 4, and 6. If surgery is scheduled after week 10 one more TG02-treatment will be given in week 10 (see [Table 6-1](#)).

In the TG02-treatment GM-CSF is to be given 15-30 minutes before TG02.

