The drug handling of TG02-treatment will be described in a separate Study Drug Handling Plan.

Table 8-1: Treatment schedule

Time point	DTH test (TG02)	TG02-treatment (GM-CSF followed by TG02)	Pembrolizumab (Part II of the study)
Week 1	X	X	
Week 2		X	
Week 3		X	
Week 4	X	X	X
Week 6	X	X	X
Week 8	X*		X***
Week 10 (only if surgery is after week 10)	X**	X	X

*If surgery is scheduled to be done in week 8, DTH (TG02) injection to be done approximately 48 hours prior to surgery.

** Only to be taken for patients who have surgery at week 10 or later and had a negative outcome at week 8.

*** If surgery is taking place Day 51-63, pembrolizumab will be given at Day 50/Week 8.

Pembrolizumab: A fixed dose of 200 mg pembrolizumab will be administered as an intravenous infusion. Pembrolizumab should be administered according to the latest version of the Summary of Product Characteristics (SmPC), and dosed according to available guidelines for the use of this drug. Dependent on time of surgery, a patient will receive pembrolizumab 2 to 4 times throughout the treatment period.

All handling of the IMPs/drug products should be in compliance with normal handling of sterile products for injections.

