9. STUDY ASSESSMENTS

9.1. Assessment of Efficacy

9.1.1. Primary Efficacy Variables

A systemic immune response is defined as having a positive in vivo DTH and/or a positive in vitro T-cell response at least once during the treatment period. Change intra-tumoural T-cells in resected tumour tissue at surgery compared to pre TG02-treatment core biopsy will be investigated.

Delayed Type Hypersensitivity (DTH)

DTH tests are performed in order to demonstrate whether a TG02 RAS mutation specific immune response has been elicited.

[figure not shown]
Administration of TG02 only (without GM-CSF or preceded by TG02-treatment) must be injected intradermally in the lower area of the contralateral arm to TG02-treatment as a Delayed Type Hypersensitivity (DTH) test.

The DTH test is administered at baseline (Day 1 before treatment) week 4, week 6 and week 10 if surgery is scheduled after week 10 and the patient has not shown positive DTH reaction.

The DTH skin reaction assessment is to be performed 48 hours (+/- 4 hours) after each administration by the patient in a study specific diary. The patient will be instructed by the study nurse how to record the DTH response and how to enter the results into the diary. The DTH-test will be considered positive if the area of the skin reaction has an average diameter* of ≥ 5 mm at the 48 hours (+/- 4 hours) assessment ([Figure 4](#)).

Figure 4: DTH Skin Reaction Registration (induration and erythema)

* Average diameter: $\frac{a \text{ mm} + b \text{ mm}}{2}$

T-cell Analyses

Immunology-processed blood samples (PBMC) will be taken at baseline (Day 1, Week 1) and week 8 (Day 50). If surgery is after week 10, a third sample will be taken as close as possible up to the date of surgery. All samples will be processed and stored under appropriate conditions until being analysed in batches to minimize day to day assay variability. PBMCs will be analysed for the presence of TG02 specific T-cells which will be described in a study specific Immune Monitoring Plan.

Tumour biopsy assessment

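### For week 8 surgery the DTH injection is set about 48 h before surgery but must be read by the patient at 44–52 h, so the last reading of a primary endpoint is at risk

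*Protocol*

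**What the plan says.** TG02-specific DTH response is a primary endpoint (Protocol 6.1), counted as any positive test during the study (Protocol 11.6.1.2; SAP 6.1.1).

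- **Time of surgery.** Protocol 6.4.2 describes surgery as one "which is planned for week 8 but can occur in a window up to week 14".
- **Injection.** For week 8 surgery, Table 6-1 footnote b has "If surgery is scheduled to be done in week 8, DTH (TG02) injection to be done approximately 48 hours prior to surgery", and the note to Table 8-1 repeats it: "DTH (TG02) injection to be done approximately 48 hours prior to surgery". Section 6.4.2 is looser: "if surgery is scheduled for week 8 the DTH test should be performed two days before surgery". The synopsis says the same: "if surgery is scheduled for week 8, the DTH test should be performed two days before surgery".
- **Reading.** Footnote j requires "Assessment of DTH (TG02) injection site to be done 48 hours (+/- 4 hours) after each DTH (TG02) injections by the patient". Section 9.1.1 agrees: "The DTH skin reaction assessment is to be performed 48 hours (+/- 4 hours) after each administration by the patient". That section also ties positivity (average diameter of at least 5 mm) to this reading.
- **Order on vaccination days.** Section 8.2 begins "Where a DTH (TG02) injection is being performed the TG02 DTH dose should be administered" and goes on to place that dose 30 minutes ahead of the TG02-treatment.
- **Late test.** Footnote i places it 48 h before surgery. Section 6.4.2, the synopsis and Table 8-1 place it at week 10.

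Section 9.1.1 omits week 8 from its own list of test times. The synopsis, Section 6.4.2 and both tables include it, so I take it as intended.

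**The concern.** Two timing rules, each reasonable alone, meet at the operation. An injection two days ahead and a reading two days after injection put the nominal reading at the moment surgery begins, and the only named reader is the patient about to undergo it. Neither document tells the patient to read before theatre, names a substitute reader, or gives a rule for a missed reading. Section 10.1 treats the DTH diary as source data, so a missed reading has no evident second record.

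The test matters because the week 6 DTH dose precedes that day's vaccination. For a patient operated on in week 8, the pre-surgery test is the only one injected after the fifth vaccination. In Part II it is also the only one injected on a day after the second pembrolizumab infusion (Day 36). Late conversion is plausible: in the four-peptide pancreatic study cited in Section 4.7, DTH responders rose from 11 after the initial 4-week cycle to 16 after two more administrations, at weeks 6 and 10.

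**Working it through.** The plan gives no figure to reproduce; this is timing arithmetic.

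**1. Reading window relative to surgery.** Inputs: lead L from injection to surgery (about 48 h; footnote b, Table 8-1) and reading at 44–52 h (footnote j, Section 9.1.1). The window runs from 44 − L to 52 − L hours relative to the start of surgery. In-window hours before surgery = max(0, min(8, L − 44)).

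| Lead L (h) | Window (h from start of surgery) | Nominal reading (h) | In-window hours before surgery |
|---|---|---|---|
| 44 | 0 to +8 | +4 | 0 of 8 |
| 46 | −2 to +6 | +2 | 2 of 8 |
| 48 | −4 to +4 | 0 | 4 of 8 |
| 50 | −6 to +2 | −2 | 6 of 8 |
| 52 | −8 to 0 | −4 | 8 of 8 |
| 72 | −28 to −20 | −24 | 8 of 8 |

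These are shares of a window, not probabilities of losing the reading.

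**2. What two days can mean.** With assumed clock times, injection at 14:00 on day −2 and theatre at 08:00 gives a lead of 42 h (24 + 18). The window then opens 2 h after surgery starts.

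**3. Who is affected.** For an injection at the Day 50 visit and the same clock hour, surgery on Day 51 gives a lead of 24 h (0 of 8), Day 52 gives 48 h (4 of 8) and Day 53 gives 72 h (8 of 8). A Day 50 test with surgery on Days 53–63 is unaffected.

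**4. Effect on the endpoint.** SAP 6.4.2 uses the analysis set as the general denominator, but available data in by-time-point tables. A patient negative on all earlier tests whose last reading is missing is therefore a non-responder overall and drops out of the week 8 row.

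- One such patient moves the Part II rate by 1/10 = 10 points, or 1/6 = 17 points at the group size in Protocol 11.1. This is only 1/n.
- In the cited study, (16 − 11)/16 = 5/16 = 31% of responders converted after the initial cycle. The protocol does not divide them between weeks 6 and 10, and a week 8 surgery patient gets no week 10 dose. If TG02 kinetics are similar, the share first turning positive after the week 6 vaccination lies between 0 and 31%.

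**5. Late test.** The Day 64 visit (± 4 days, Section 6.4) covers Days 60–68. Footnote i puts the injection at surgery day − 2, so both rules hold for surgery on Days 62–70. Within Days 65–92 (28 days) that leaves Days 65–70, or 6 days; the rules conflict on 28 − 6 = 22. Table 8-1 and the notes to Figures 2 and 3 say week 10 or later. That adds Day 64, where both rules can be met, giving 22 of 29. These are calendar days, not patients.

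**The case against.** A reader might infer that the reading is lost, or that half its window is post-operative. The documents do not support either. The second half follows the start of surgery, and at the stated lead a reading at 44–48 h is both pre-operative and in tolerance. The lead is given as approximate, and Section 9.1.1 has the study nurse instruct the patient; that instruction and the diary are not among the documents and may already cover the point.

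The SAP is also more forgiving than the protocol. SAP 6.1 and 6.1.1 count a test as positive when erythema and/or induration is recorded as positive on the eCRF, with no hour limit. A reading a few hours early could still count in the efficacy set. It would leave the per protocol set only if the out-of-window deviation were graded major (SAP 4.4).

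Nor do the figures above measure an expected bias. Harm to the overall count needs week 8 surgery, negative earlier tests, conversion at this test only, and a missed reading. Section 4.8 expects responses after 4–6 weeks of vaccination, when the unaffected week 4 and week 6 tests are given. The composite systemic response also accepts a positive T-cell result, and all analysis is descriptive.

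All of this stands and limits the consequence. It does not remove the conflict: for the planned time of surgery, the written rule aims the reading at the moment when the patient is least able to make it.

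**Conclusion.** The point holds as a scheduling conflict that puts the reading at risk. At the stated 48 h lead, 4 of the 8 window hours fall after surgery starts; at 44 h or less all 8 do. The effect on the overall DTH count is confined to patients who were negative throughout and would first convert at this test. Their number cannot be derived from the documents. The 0–31% is a ceiling that assumes similar kinetics to the cited study, and the 10–17 points is the weight of one patient. The documents do not support a claim that the primary endpoint is invalid or biased by a stated amount. The change is still worth making because it is cheap and protects the only test injected after the week 6 vaccination. Section 4.2 reports four patients already treated, so an amendment would act mainly on Part II.

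The disagreement over the late test is a separate inconsistency and adds no weight to the week 8 point. It does matter for patients still DTH-negative: a Day 64 test is injected before the week 10 vaccination, whereas a test tied to later surgery can follow it.

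**What to change.** **Week 8 surgery.** Amend footnote b, Table 8-1, Section 6.4.2, the synopsis and the diary instruction so that:

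- the injection is given at least 52 h before scheduled surgery, in practice on day −3;
- the reading is completed at 44–52 h and before the patient goes to theatre;
- footnote e is widened from 2–0 to 3–0 days, so that PBMC is still drawn before the TG02 injection at that visit, as footnote h requires.

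Where only day −2 is possible, require a lead of at least 48 h and a reading at 44–48 h before theatre. This is the fallback because, with theatre at an assumed 08:00 and a 48 h lead, the slot is 04:00–08:00 on the day of surgery. Injection at 10:00 on day −3 instead gives a reading slot of 06:00–14:00 on day −1.

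The cost is slightly tighter pre-operative scheduling and a PBMC draw one day earlier. No extra patients or assays are needed.

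**Late test.** Choose one time for all patients and align footnote i, Section 6.4.2, the synopsis and Table 8-1. Day 64 matches most of the text, but the test then comes 30 minutes before TG02-treatment and no DTH test follows the week 10 vaccination. A pre-surgery test keeps one when surgery is late enough (with a Day 64 vaccination and a day −3 injection, surgery from Day 68, since 68 − 3 = 65), but it needs the same lead of at least 52 h. The sponsor should state which it wants and accept the corresponding loss.
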